#### 12.5.3 Multi-variable extension

The above method extends naturally to multivariable models described below, where a standardized association is computed by multiplying the generalized Wald statistic by the number of "phase 2 ptids".

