## 12.5 Univariate CoR: evaluating markers as endpoints

## 12.5.1 Objective

Follmann (2018) describe a method for comparing two endpoints in terms of the sample size required to power a future study. In this approach, we imagine that our goal is to compare two (or more) markers in terms of their standardized effect size. Markers with stronger correlates signals will have higher standardized effect sizes. We then present the comparison of effect sizes in terms of a sample size ratio. For example, if the ratio of standardized effect size for Day 57 binding Ab to Spike compared to Day 57 pseudovirus neutralization ID50 is 2, then a future correlates study would need to enroll twice as many participants to achieve a similar power to reject the correlates null hypothesis for the inferior marker. The method provides, in essence, a more interpretable means of comparing the magnitude of p-values for different markers.

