## 12.5.2 Approach

We will apply the approach to the univariate Cox models. The required output for the method of Follmann (2018) is the same as for the IPWCC Cox regression described above. For each marker, the Wald statistic for the associated log hazard ratio is divided by the square root of the harmonic mean of cases and non-cases in the phase 2 dataset to obtain the standardized association. Denote by  $\hat{\Delta}_m$  the standardized association for the *m*-th marker. We define the comparison of the  $\ell$ -th and *m*-th marker's standardized association to be  $\hat{\omega}_{\ell,m} = \hat{\Delta}_{\ell}/\hat{\Delta}_m$ . This is mapped into an estimated ratio of sample sizes

 $\theta_{\ell,m}$  via the following relationship

$$\hat{\theta}_{\ell,m} = \begin{cases} \hat{\omega}_{\ell,m}^2 & \text{if } \hat{\Delta}_{\ell} < 0 \text{ and } \hat{\Delta}_m < 0\\ 0 & \text{if } \hat{\Delta}_{\ell} > 0 \text{ and } \hat{\Delta}_m < 0\\ \text{undefined } \text{if } \hat{\Delta}_{\ell} > 0 \text{ and } \hat{\Delta}_m > 0\\ \infty & \text{if } \hat{\Delta}_{\ell} < 0 \text{ and } \hat{\Delta}_m > 0 \end{cases}$$

A 95% confidence interval for  $\theta_{\ell,m}$  can derived based on the bootstrap, though some cared is needed to handle edge cases. Follmann (2018) describe the following approach. For the *b*-th bootstrap sample (generated, as described above), we compute  $\hat{\Delta}_{\ell}^{(b)}$ ,  $\hat{\Delta}_{m}^{(b)}$ , and  $\hat{\omega}_{\ell,m}^{(b)}$  as described above. We then define separate "versions" of  $\hat{\theta}_{\ell,m}^{(b)}$ ,

$$\hat{\theta}_{\ell,m}^{(b)}(L) = I(\hat{\Delta}_{\ell} < 0, \hat{\Delta}_{m} < 0)(\hat{\omega}_{\ell,m}^{(b)})^{2} + I(\hat{\Delta}_{\ell} < 0, \hat{\Delta}_{m} > 0) \times \infty$$
$$\hat{\theta}_{\ell,m}^{(b)}(U) = I(\hat{\Delta}_{\ell} < 0, \hat{\Delta}_{m} < 0)(\hat{\omega}_{\ell,m}^{(b)})^{2} + I(\hat{\Delta}_{\ell} > 0, \hat{\Delta}_{m} > 0) \times \infty$$
$$+ I(\hat{\Delta}_{\ell} < 0, \hat{\Delta}_{m} > 0) \times \infty$$

The lower bound of the bootstrap 95% confidence interval is the 2.5-th percentile of the bootstrap distribution of  $\hat{\theta}_{\ell,m}^{(b)}(L)$ ; the upper bound of the bootstrap 95% confidence interval is the 97.5-th percentile of the bootstrap distribution of  $\hat{\theta}_{\ell,m}^{(b)}(U)$ .

We will compare ratios of sample sizes of the following markers:

- 1. binding Ab RBD vs. pseudovirus neutralization ID50

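### Section 12.5: the worked example, the bootstrap interval and the multivariable extension of the marker sample-size ratio each contain a formula error

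*Combined protocol and SAP*

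**What the plan says.** Section 12.5.1 illustrates the method with a hypothetical case: "if the ratio of standardized effect size for Day 57 binding Ab to Spike compared to Day 57 pseudovirus neutralization ID50 is 2". The stated consequence reads: "then a future correlates study would need to enroll twice as many participants", so that the inferior marker has similar power.

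Section 12.5.2 defines the quantities. The scaling, done marker by marker, is this: "the Wald statistic for the associated log hazard ratio is divided by the square root of the harmonic mean of cases and non-cases". Both counts come from the phase 2 data, and the result is a signed standardized association Delta. The ratio of two Deltas is omega, and the sample-size ratio theta follows by cases:

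- both Deltas negative: omega squared;
- first positive, second negative: 0;
- first negative, second positive: infinity;
- both positive: undefined.

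For the 95% interval, Delta and omega are recomputed in each bootstrap replicate b. A lower and an upper version of theta are then formed, which differ in how they treat the sign combinations. In both printed formulas theta and omega carry the superscript (b), but the Deltas inside the sign indicators do not.

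Three univariable comparisons are listed: RBD binding with pseudovirus ID50, RBD binding with MN50, and ID50 with MN50.

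Section 12.5.3 extends the method to the multivariable Cox models of 12.7 in one sentence: "a standardized association is computed by multiplying the generalized Wald statistic by the number of" phase 2 participants. It states no new mapping and lists no comparisons.

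**The concern.** The three subsections should describe one calculation, and they do not. The example contradicts the formula it illustrates. The bootstrap interval is introduced as needing care in edge cases, yet its printed indicators cannot respond to them when both original estimates are negative. The extension puts an unsigned quadratic statistic into a rule built for a signed linear one.

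Section 12.2 describes the main CoR analyses as automated and reproducible. If 12.5 is programmed in the same way from its printed formulas, the univariable intervals can be wrong when a marker is weakly associated, and the multivariable comparison yields no number. A reader who plans from 12.5.1 would halve the required sample size.

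**Working it through.** **1. Worked example (12.5.1 against 12.5.2).** Delta is a Wald statistic divided by the square root of a sample size, so it is an effect per square-root participant. Equal power needs Delta × sqrt(N) to be equal for both markers, hence N ratio = omega squared.

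- Stated: omega = 2, ratio 2.
- From 12.5.2: theta = 2² = 4. A ratio of 2 would need omega = sqrt(2) = 1.41.
- Cross-check with standard formulas (two-sided 0.05, 80% power, effect halved): 1570 against 393 for a comparison of means, and 349 against 88 events for a Cox coefficient. The ratios are 3.99 and 3.97. Sixteen variants of test side, alpha and power gave 3.97 to 4.00.
- Power of the inferior marker with only twice the participants: where the better marker has 80%, Φ((1.960 + 0.842)/sqrt(2) − 1.960) = Φ(0.02) = 51%. Where it has 90%, Φ((1.960 + 1.282)/sqrt(2) − 1.960) = Φ(0.33) = 63%.

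**2. Bootstrap interval (12.5.2).** If both original Deltas are negative, the printed indicators equal 1 for the first term and 0 for all others, in every replicate. Both versions reduce to the replicate omega squared, whatever the replicate signs.

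With replicate signs, the upper version is infinite whenever the second marker's replicate Delta is positive, and the lower version is 0 whenever the first marker's is. If the replicate Wald statistics are roughly normal with unit variance, the upper limit is therefore infinite once Φ(z of second marker) exceeds 2.5%, that is, once |z| is below 1.96.

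The Wald values and correlations below are assumptions, because the documents give none. Replicates are bivariate normal.

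| z first / second | Correlation | Interval as printed | Interval with replicate signs |
|---|---|---|---|
| -3 / -1.8 | 0.7 | upper about 130 | upper infinite (3.6% of replicates flip the second marker) |
| -2.2 / -2.0 | 0.8 | upper about 14 | upper several hundred |
| -2.5 / -1.5 | 0.8 | 0.60 to 190 | 0.72 to infinite |
| -1 / -2 | 0.95 | 0.002 to 14 | 0 to 0.89 |
| -3 / -3 | 0.8 | 0.34 to 2.93 | 0.34 to 2.95 |
| -4 / -4 | 0.8 | 0.49 to 2.02 | 0.49 to 2.02 |

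In the second row about 2.3% of replicates are infinite, just under 2.5%. The corrected limit therefore sits in an unstable tail (roughly 270 to 390 across runs), and no exact figure should be read from it.

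**3. Multivariable extension (12.5.3).**

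- *Sign.* A generalized Wald statistic W is a quadratic form and cannot be negative. Multiplied by a count, it stays non-negative. With both Deltas positive, 12.5.2 returns undefined; all 20,000 simulated comparisons of a three-marker with a two-marker model did so. The printed bootstrap formulas then give 0 for the lower and infinity for the upper version in every replicate, so the interval is always 0 to infinity.
- *Scale.* Even with signs ignored, W is already squared. For W = 16 and 8 on the same data and degrees of freedom, the sample-size ratio is 16/8 = 2, but omega squared gives (16/8)² = 4.
- *Standardization.* At constant signal W grows in proportion to n. Doubling n doubles W, so W × n rises fourfold while W/n is unchanged. The common factor cancels in the ratio only when both models use the same phase-two set.

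**The case against.** **Importance.** A reader might infer that 12.5 is the plan's main basis for choosing between binding and neutralizing markers. The documents do not support that. Section 12.6 compares assays by CV-AUC and variable importance, Section 16.1 gives that analysis special weight in ranking markers, and 12.5 is absent from the outline in 12.2, the multiplicity plan in 12.4.2 and Table 10. This objection stands: the section is supportive.

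**Bootstrap.** The missing superscript is probably a notation slip, since the text computes replicate Deltas and mixed-sign terms make sense only per replicate. It also does not always shorten intervals: at -2.5/-1.5 the printed lower limit is the wider one, and at -1/-2 with correlation 0.95 the printed upper limit is far too large. Both points stand. They limit the claim to wrong intervals for weak markers; they do not make the printed formula right. Superscripts survive on theta and omega in the same lines, so lost characters are an unlikely explanation.

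**Extension.** Section 12.5.3 names no comparisons and could be called merely under-specified. A multivariable model set against a single marker with negative Delta would give 0 or infinity, not undefined. That is correct but no more informative. The factor n does cancel for models on one phase-two set, and 12.6.3 aims at a single set. However, the Day 29 and Day 57 models of 12.7.3 use different case sets, and Section 20 excludes antiretroviral-positive participants only from analyses that include pseudovirus neutralization.

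**Example.** It is only illustrative, and the operative formula is sound. That is true, but the two still contradict each other.

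**Conclusion.** All three errors hold on the printed text.

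- The example understates the sample-size ratio by a factor of two (2 stated, 4 by the plan's own mapping).
- The bootstrap formulas ignore replicate sign flips when both original estimates are negative. Under the assumed normal replicates this matters when at least one Wald statistic is about 2 or less in absolute value, and not at -3/-3 or stronger. Weak associations are plausible, since Table 4 allows Cox analyses from 25 vaccine cases.
- Any comparison of two multivariable models is undefined if the 12.5.2 mapping carries over, and no other mapping is given.

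The consequences stay within 12.5. Cox hazard ratios, their p-values and the multiplicity adjustment do not use these formulas. The documents also do not show whether any program uses the original-sample signs. The correction should be made because it is cheap and the formulas as written give wrong or no results.

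**What to change.** 1. **12.5.1:** replace twice by four times, or state the 2 as the ratio of sample sizes instead of effect sizes. The authors should say which was meant.
2. **12.5.2:** put the superscript (b) on both Deltas in every indicator of the lower and upper versions.
3. **12.5.3:** define the standardized association as the generalized Wald statistic divided by the harmonic mean of cases and non-cases, and take theta as the plain ratio of two such values, unsquared and with no sign rule. For single markers with negative associations this agrees with 12.5.2, because W = z² and (z²/H) is Delta squared, where H is the harmonic mean. With z = -3 and -1.8 on the same data both give 9/3.24 = 2.78.
4. **12.5.3:** list the intended model comparisons, and say how models with different numbers of markers are compared. Subtracting the degrees of freedom from W and truncating at zero is not a ready answer. It gives (9 − 1)/(3.24 − 1) = 3.57 in the same example, so it departs from 12.5.2, and it becomes 0/0 when both statistics fall at or below their degrees of freedom.

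The cost is a few lines of text and a check of the corresponding code. No new data are needed.

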## 12.6 Multivariable CoR: Superlearning of Optimal Risk Prediction Models

#### 12.6.1 Objectives

The multivariable CoR objective is addressed through two sub-objectives: first to build an 'estimated optimal surrogate' (Price et al., 2018), a model that best predicts the outcome from Day 57 antibody markers and baseline factors. The second sub-objective is estimation and inference on variable importance measures for each Day 57 antibody marker, for ranking of antibody markers by their importance/influence on predicting risk. The analysis plan is patterned off of the analysis of the HVTN 505 HIV-1 vaccine efficacy trial (Neidich et al., 2019). For these analyses both baseline-subtracted and nonbaseline subtracted versions of the Day 57 markers are used, in a broader unbiased analysis to build models most predictive of outcome.

#### 12.6.2 Input variable sets

Day 57 antibody markers are classified into the following four antibody marker variable sets, with individual variables listed within categories:

- 1. Binding antibody anti-Spike (S-bAb)
  - a Day 57 anti-Spike IgG concentration
  - b delta (Day 57 Day 1) anti-Spike IgG concentration
  - c indicator 2FR anti-Spike IgG concentration
  - d indicator 4FR anti-Spike IgG concentration
- 2. Binding antibody anti-RBD (RBD-bAb)
  - a Day 57 anti-RBD concentration
  - b delta (Day 57 Day 1) anti-RBD concentration
  - c indicator 2FR anti-RBD concentration
  - d indicator 4FR anti-RBD concentration
- 3. Pseudovirus neutralizing antibody anti-Spike (pseudovirus-nAb)
  - a Day 57 anti-Spike ID50

- b Day 57 anti-Spike cID80
- c delta (Day 57 Day 1) anti-Spike ID50
- d delta (Day 57 Day 1) anti-Spike cID80
- e indicator 2FR anti-Spike ID50
- f indicator 4FR anti-Spike ID50
- g indicator 2FR anti-Spike cID80
- h indicator 4FR anti-Spike cID80
- 4. Wild Type Live virus neutralizing antibody anti-Spike (WT live virusnAb)
  - a Day 57 anti-Spike MN50
  - b delta (Day 57 Day 1) anti-Spike MN50
  - c indicator 2FR anti-Spike MN50
  - d indicator 4FR anti-Spike MN50

The baseline factors without any marker data constitutes another set of variables to include in the superlearner modeling.

#### 12.6.3 Missing data

We expect a very small amount of missing data from the five antibody marker types (bAb Spike, RBD; pseudovirus-nAb ID50, cID80; WT live virus-nAb MN50). However, there may be a small amount of missing data, with possibly different participants missing data for different markers. We take the following approach to handle any missing data that occurs.

First, we define the two-phase sampling indicator  $\epsilon$  as taking value of one if a participant has Day 1 and Day 57 bAb data for both Spike and RBD, where here we assume that the MSD platform is highly robust such that it will have nearly 100% complete data for sampled participants. Second, for the other three marker types (pseudovirus-nAb ID50, cID80; WT live virus-nAb MN50), for participants with  $\epsilon = 1$  but the Day 1 and/or Day 57 marker value is missing, we use single imputation to fill in any missing values, ignoring the uncertainty in the imputations in the analysis, because it should have negligible impact on results given the (very) small amount of missing data. Multiple linear regression will be used to impute missing values, separately for each antibody marker, based on the set of individuals with that antibody marker measured at Day 1 and 57. Accurate imputations are possible given the high correlations of the markers, especially between ID50 and cID80 within the same immunoassay. This process means that the two-phase data set has a simple 'all-or-nothing' missing data pattern where participants with  $\epsilon = 1$  have all markers with Day 1 and Day 57 data, and are included in IPWCC analyses, and participants with  $\epsilon = 0$  have some or all markers missing and are excluded from IPWCC analyses. This means that all IPWCC data analyses can use the same empirical frequency (IPS) sampling weights.

For analysis methods that use the whole cohort (phase-one plus phase-two data), the same phase-two data as described above are used. If some of the phase-one baseline factors that are adjusted for variables are missing with only a small amount of missing values, then single imputation will be used to fill in the values, and, as for the immunologic marker imputations, the uncertainty in the imputations will be ignored in the analyses. Simple average values will be used to fill in baseline covariate missing values of the baseline factors.

## 12.6.4 Implementation of superlearner

For baseline risk score development, Superlearner is applied to the placebo arm only, as mentioned in Section 10. For multivariable immune correlates of risk/estimated optimal surrogate development, Superlearner is applied to the vaccine arm only. The following details are used in the implementation of superlearner of the vaccine arm only:

- Pre-scale each quantitative and ordinal variable to have empirical mean 0 and standard deviation 1.
- For the immune correlates analysis, the final library of learners is selected

accounting for the number of phase-two endpoint cases in the vaccine arm. If the number of cases is limited, at or near 25 evaluable endpoint cases, then the modeling will only allow learning algorithms to have a maximum of 5 Day 57 antibody marker variables, and will use leaveone-out cross-validation and the negative log-likelihood loss function, a combination that tends to provide good performance in small sample size settings. On the other hand, if there are larger numbers of endpoint cases in the vaccine arm, then 5-fold cross-validation will be used, and no more than floor( $n_v/6$ ) input variables will be used in the model where  $n_v$  is the number of evaluable vaccine endpoint cases. The choices will be finalized prior to case/control unblinded analysis.

- Include learning algorithms with and without screening of variables. Screens used will be: 1) glmnet (lasso) pre-screening (with default tuning parameter selection), 2) logistic regression univariate 2-sided p-value screening (at level p < 0.10), and 3) high-correlation variable screening (described below). The adaptive algorithms (SL.randomForest, SL.xgboost, SL.gam, SL.polymars) are only used with these screens, given that the limited number of endpoint cases may challenge use of these methods with no variable screening. Moreover, the adaptive algorithms are not used if there are only 25 (or close to it) endpoint cases. All of the selected learners are coded into the SuperLearner R package available on CRAN.
- Include high-correlation variable screening, not allowing any pair of input variables to have Spearman rank correlation r > 0.9. When a pair of variables has r > 0.9, the variable with the highest ranked signal-to-noise ratio (i.e., biological dynamic range) is selected; if these data are not available or there is a tie then variables are selected in the following order of priority: first WT live virus-nAb, second pseudovirus-nAb, third bAb.
- The superlearner is conducted averaging over 10 random seeds, to make results less dependent on random number generator seed.
- All of the learners are implemented with IPS weighting, using the weights  $\hat{w}_{57.x}$  defined in Section 12.3.1 to account for the two-phase sampling

design.

- Two levels of cross-validation are used:
  - Outer level: CV-AUC computed over 5-fold cross-validation repeated 10 times to improve stability
  - Inner level: leave-one-out CV used to estimate ensemble weights (if  $n_v$  is near 25) and 5-fold CV if  $n_v$  is larger.
- Results for comparing classification accuracy of different models are based on point and 95% confidence interval estimates of cross-validated area under the ROC curve (CV-AUC) and difference in CV-AUC as a predictiveness metric (Hubbard et al., 2016; Williamson et al., 2020). Results are presented as forest plots of point and 95% confidence interval estimates similar to those used in Neidich et al. (2019) (Figure 3) and Magaret et al. (2019). CV-AUC is estimated using the R package *vimp* available on CRAN, including the IPS weights that are used for other data analyses.

For the baseline risk score SuperLearner analysis of the placebo arm (Section 10), the same approach is used, with the following modifications: (1) 5-fold cross-validation will be used with no more than  $\max(20, \operatorname{floor}(n_p/20))$  input variables included in each model, where  $n_p$  is the number of evaluable placebo arm cases; (2) no IPS weighting is needed; (3) the adaptive learning algorithms are included.

Table 7 lists the learning algorithms that are applied to estimate the conditional probability of the outcome based on the input variable sets considered above. Most of the algorithms are non-data-adaptive type learning algorithms, such as parametric regression models (e.g., generalized linear models [glms]), which are simple, stable, and advantageous for an application with a limited number of endpoint events. Data-adaptive type algorithms are also included if the number of endpoint events is high enough, for increasing flexibility of modeling and reducing the risk of model misspecification: SL.ranger, SL.gam, SL.polymars, and SL.xgboost. All of the selected learners are coded into the SuperLearner R package. Before fitting the superlearner models to the vaccine arm data, a decision will be made on how to define the "baseline risk factors" input variable set, based on prediction-accuracy results of the Superlearner analysis that built the baseline behavioral risk score based on the placebo arm, as well as on external knowledge of important individual risk factors. The set of baseline risk factors will include a subset of individual risk factors and/or the baseline risk score itself.

For the immune correlates objective the superlearner model is fit to each of the following 12 variable sets, with immunological variables listed in Section 12.6.2:

- 1. Baseline risk factors
- 2. Baseline risk factors and the Day 57 bAb anti-Spike markers
- 3. Baseline risk factors and the Day 57 bAb anti-RBD markers
- 4. Baseline risk factors and the Day 57 pseudovirus-nAb ID50 markers
- 5. Baseline risk factors and the Day 57 pseudovirus-nAb cID80 markers
- 6. Baseline risk factors and the Day 57 live virus-nAb MN50 markers
- 7. Baseline risk factors and the Day 57 bAb markers and the Day 57 pseudovirus-nAb ID50 markers
- 8. Baseline risk factors and the Day 57 bAb markers and the Day 57 pseudovirus-nAb cID80 markers
- 9. Baseline risk factors and the Day 57 bAb markers and the Day 57 live virus-nAb MN50 markers
- 10. Baseline risk factors and the Day 57 bAb markers and the combination scores across the five markers [PCA1, PCA2, FSDAM1/FSDAM2 (the first two components of nonlinear PCA), and the maximum signal diversity score He and Fong (2019)].
- 11. Baseline risk factors and all individual Day 57 marker variables
- 12. Baseline risk factors and all individual Day 57 marker variables and all combination scores (full model)

Therefore in total, 12 variable sets are studied. The reason to include the first variable set is to investigate how much incremental improvement in predicting outcome is obtained by adding antibody marker variables on top of baseline demographic/exposure factors. The other variable sets are designed to compare the four immunoassay types by their predictiveness, to compare the two pseudovirus neutralization readouts ID50 and cID80 for their predictiveness, and to investigate incremental predictive value in using multiple immunoassays. The final variable set is included as the full model that considers all variables together, which serves as another reference model.

Table 7: Learning Algorithms in the Superlearner Library of Estimators of the Conditional Probability of Outcome, for Building the Baseline Risk Score Based on the Placebo Arm^1.

	Scroons/
	Screens
Algorithms	Tuning Parameters
SL.mean	None
$\mathrm{SL.glm}$	Low-collinearity and (All, Lasso, $LR)^2$
SL.bayesglm	Low-collinearity and (All, Lasso, LR)
SL.glm.interaction	Low-collinearity and (All, Lasso, LR)
SL.glmnet	(alpha=1; All)
SL.gam	Low-collinearity and (Lasso, LR)
SL.ksvm	Low-collinearity and (kernel="rbfdot", "polydot") and (Lasso, LR)
SL.polymars	Low-collinearity and (Lasso, LR)
$SL.xgboost^3$	All and $(maxdepth, shrinkage, balance) = (4, 0.1, no)$
SL.ranger 	All and balance $=$ no

All continuous and ordinal covariates are pre-standardized to have empirical mean 0 and standard deviation 1.

All = include all variables; Lasso = include variables with non-zero coefficients in the standard implementation of SL.glmnet that optimizes the lasso tuning parameter via cross-validation; Low-collinearity = do not allow any pairs of quantitative variables with Spearman rank correlation > 0.90; LR = Univariate logistic regression Wald test 2-sided p-value < 0.10.

 Covariate balancing (if requested) is done using option scale\_pos\_weight in SL.xgboost and option case.weights in SL.ranger.

Table 8: Learning Algorithms in the Superlearner Library of Estimators of the Conditional Probability of Outcome: Simplified Library in the Event of Fewer than 50 Vaccine Breakthrough Cases for an Analysis, for Use in Multivariable CoR Analysis of Moderna COVE.

	Screens/
Algorithms	Tuning Parameters
SL.mean	None
$\mathrm{SL.glm}$	Low-collinearity and (All, Lasso, $LR)^2$
SL.glmnet	(All, alpha=0) $(All, alpha=1)$
SL.xgboost	$(maxdepth, shrinkage, balance^3) = (2, 0.1, yes) (2, 0.1, no) (4, 0.1, yes) (4, 0.1, no)$
SL.ranger	balance = (yes, no)

 ${}^{2}$ **All** = include all variables; **Lasso** = include variables with non-zero coefficients in the standard implementation of SL.glmnet that optimizes the lasso tuning parameter via cross-validation; **Low-collinearity** = do not allow any pairs of quantitative variables with Spearman rank correlation > 0.90; **LR** = Univariate logistic regression Wald test 2-sided p-value < 0.10.

Covariate balancing (if requested) is done using option scale\_pos\_weight in SL.xgboost and option case.weights in SL.ranger.

Given the class-imbalance issue, with many more non-case than case records, all of the cross-validation for the multivariable immune CoR objective is done stratified by case/non-case status.

In order to evaluate the relative performance of the superlearner estimated models for each of the 12 variable sets, derived using the learning algorithms specified in Table 7, the CV-AUC is estimated with a 95% confidence interval (Hubbard et al., 2016; Williamson et al., 2020). The point and 95% confidence interval estimates of CV-AUC are reported in a forest plot, which provide a way to discern which Day 57 antibody assays and readouts/markers provide the most information in predicting COVID or other outcomes. The specified library of learners may be modified prior to SAP finalization (before breaking the blind of case/non-case status).

As noted above CV-AUC is estimated using the R package *vimp* available on CRAN, which uses augmented inverse probability weighting to properly estimate CV-AUC accounting for the two-phase sampling design.

If there are fewer than 50 vaccine breakthrough cases included in a correlates analysis, then the libary of learners will be simplified to that specified in

